1 PROTOCOL SUMMARY

[figure not shown]
1.1 SYNOPSIS

Title:	A Phase II, open-label randomized study of immediate prostatectomy vs. cabozantinib followed by prostatectomy in men with high-risk prostate cancer.
Study Description:	Subjects will be assigned (Safety Lead-In Cohort) or randomized to either: (1) cabozantinib 40 mg PO daily for 4 weeks, followed by a 2 week drug washout period before prostatectomy (n = 20), or (2) immediate prostatectomy (n = 10). The Safety Lead-In Cohort will consist of 6 subjects receiving cabozantinib prior to prostatectomy. The randomized portion will consist of the remaining cabozantinib prior to prostatectomy subjects (n=14) and immediate prostatectomy subjects (n=10).
Primary Objective:	To compare pathologic apoptotic indices (cleaved caspase-3) in prostatectomy specimens from patients who undergo immediate prostatectomy (controls) versus those treated with cabozantinib followed by prostatectomy.
Secondary Objective:	To conduct immune phenotypic profiling on the peripheral blood and tumor microenvironment in prostatectomy specimens from patients who undergo immediate prostatectomy versus those treated with cabozantinib prior to prostatectomy.
Exploratory Objectives:	
 1. To estimate the pathologic complete response rate (pCR) and \leqpathologic T2 (\leqpT2) rate in each arm. 2. To evaluate relapse-free survival in each arm. 3. To compare apoptosis (TUNEL), proliferation (Ki-67), and microvessel density (CD31) indices in prostatectomy specimens from patients who undergo immediate prostatectomy versus those treated with cabozantinib prior to prostatectomy. 4. To measure expression levels of c-MET, VEGF, and HGF, as well as activation status of c-MET in prostate tissue. 5. To describe changes in plasticity signaling markers associated with prostate tumors, including vimentin, AR, SNAIL, AXL, and N-cadherin with cabozantinib exposure. 6. To evaluate PTEN and p53 genomic and protein expression status in tumor tissue 7. To demonstrate that cabozantinib is safe and tolerable in patients undergoing radical prostatectomy. 8. To demonstrate that surgery is safe and feasible in patients undergoing treatment with cabozantinib. 9. To collect plasma angiome samples (multiplex ELISA) for analysis and correlation with primary and key secondary endpoints. 10. To describe gene expression patterns (in particular those associated with apoptosis, androgen receptor signaling, c-MET activation, and a c-MET-specific endocytosis panel) correlated with cabozantinib administration using RNA sequencing.

	
 11. To explore changes in serum and intratumoral androgen concentrations related to cabozantinib treatment. 12. To collect cell-free DNA (cfDNA) for analysis and correlation with primary and key secondary endpoints.
Endpoints:	
Primary: Apoptotic index by cleaved caspase-3
 
Secondary: Description of immune biomarkers, including:
 
 • Immune phenotyping of paired peripheral blood and tumor tissue: Myeloid-derived suppressor cells (MDSCs), neutrophils, M1 macrophages, and M2 macrophages in tumor tissue • Immunohistochemical (IHC) analysis of CD8+, programmed death ligand-1 (PD-L1), cytotoxic T-lymphocyte-associated protein 4 (CTLA-4), interleukin-1 receptor antagonist (IL-1RA) and B7H3 in tumor tissue • Neutrophil chemotactic factors (CXCL12 and HMGB1) and MDSC-promoting cytokines (CCL5, CCL12, CD40) in tumor tissue 
Exploratory:
 
 1. Rates of pCR and \leqpT2 2. Relapse-free survival rate at 3 years 3. Quantification of TUNEL, Ki-67, and CD31 staining 4. Quantification of c-MET, VEGF, HGF, and activated c-MET in prostatectomy tissue 5. Correlation of vimentin, AR, SNAIL, AXL, and N-cadherin with cabozantinib exposure 6. Measurement of PTEN and p53 genomic and protein expression status in tumor tissue 7. Adverse events by CTCAE v5.0, dose intensity of cabozantinib 8. Blood loss at prostatectomy and duration of hospital stay 9. Angiome biomarkers 10. Gene expression patterns using RNA sequencing 11. Serum and intratumoral androgen concentrations 12. Alterations in cfDNA
Study Population:	Eligible patients will have histologic evidence of adenocarcinoma of the prostate and be deemed candidates for curative radical prostatectomy. They will have intermediate-or high-risk, clinically localized disease and have not received prior treatment for prostate cancer.
Phase:	Phase II
Description of Sites/Facilities Enrolling Participants:	This is a multicenter study of 30 evaluable subjects. Duke is the lead site for this trial. Subjects who do not receive 21 out of 28 days of planned study drug administration and proceed to radical prostatectomy within 14 (+3) days of their last dose of study drug (Arm A only) or do not proceed to radical prostatectomy (Arm B only) will be replaced. There will be a second site selected TBD.
Description of Study Intervention:	Patients will be assigned (Safety Lead-In Cohort) or randomized to either: (1) cabozantinib 40 mg PO daily for 4 weeks, followed by a 2 week drug

	washout period before prostatectomy (n = 20), or (2) immediate prostatectomy within 12 weeks of registration (n = 10). The Safety Lead-In Cohort will consist of 6 subjects receiving cabozantinib prior to prostatectomy. The randomized portion will consist of the remaining cabozantinib prior to prostatectomy subjects (n=14) and immediate prostatectomy subjects (n=10).
Study Duration:	We estimate an accrual period of 1 year, with last patient last visit at 22 months and final report at 25 months.
Participant Duration:	Screening Phase: Six weeks (42 days) Treatment Phase (including prostatectomy) 
 • Arm A (cabozantinib): up to 85 days • Arm B (immediate prostatectomy): 1 day Follow-up Phase: 3 years post-prostatectomy for relapse-free survival

1.2 SCHEMA

2 INTRODUCTION

2.1 INTRODUCTORY STATEMENT

Prostate cancer is the most common cancer and second leading cause of cancer death in men, with approximately 165,000 new cases and 29,000 deaths in 2018¹. Radiotherapy and radical prostatectomy have been the gold standards for primary treatment of localized disease. Androgen deprivation therapy (ADT; lowering of serum testosterone to <50 ng/dl) is used for localized prostate cancer in combination with radiotherapy, biochemically recurrent (M0) prostate cancer after primary therapy (both with and

without radiotherapy), and for metastatic castration-sensitive prostate cancer (mCSPC). In contrast, neoadjuvant ADT has not shown benefit over prostatectomy alone and adjuvant ADT post-prostatectomy is controversial. After prostate cancer recurrence ADT is typically continued intermittently or continuously life-long². Both docetaxel and abiraterone acetate plus prednisone have recently demonstrated benefits when added to ADT for mCSPC³. Enzalutamide and apalutamide have both been approved for M0 castration resistant prostate cancer (CRPC)⁴. Five therapies, including an immunotherapy, two androgen receptor signaling inhibitors, two cytotoxic chemotherapies, and a radiopharmaceutical, are approved for metastatic (M1) CRPC: sipuleucel-T, abiraterone plus prednisone, enzalutamide, docetaxel, cabazitaxel, and radium-223⁵.

Aside from sipuleucel-T, which improves overall survival without inducing measurable tumor regression, there are no immunotherapies approved for prostate cancer. Immune checkpoint inhibitors (ICIs) have demonstrated substantial benefits and have been approved in multiple other solid tumors; however, they have not shown benefit in prostate cancer: a large phase II study of the PD-1 inhibitor pembrolizumab demonstrated an overall response rate of just 5%⁶ and two phase III studies of the CTLA-4 inhibitor ipilimumab failed to meet their primary endpoint of improving overall survival^{7,8}. However, in both studies there were other signs of antitumor activity in a specific subset. The prevailing conventional wisdom is that prostate cancer is generally a “cold” tumor and so, for ICIs to demonstrate benefit, either subsets of “hot” tumors must be selected or ICIs must be combined with other therapies that render the tumor more “hot” by affecting different parts of the cancer immunity cycle. Preclinically, cabozantinib has been shown to target myeloid-derived suppressor cells (MDSCs) and synergize with ICIs (cocktail of anti-PD-1 and anti-CTLA4 antibodies) in a CRPC model⁹. Cabozantinib has also been demonstrated to eradicate tumors in a PTEN/p53-deficient murine prostate cancer model through activation of neutrophil-mediated antitumor innate immunity¹⁰. Cabozantinib has demonstrated single agent activity in prostate cancer in a phase II study¹¹. Cabozantinib was also tested in a phase III randomized (2:1) trial in men with progressive mCRPC after docetaxel and abiraterone plus prednisone and/or enzalutamide (N=1,028). Although cabozantinib failed significantly improve overall survival, its activity was demonstrated as measured by bone scan response, radiographic progression free survival, symptomatic skeletal related events, circulating tumor cell conversions, and bone biomarkers¹². Thus, since neither cabozantinib nor ICIs have improved overall survival alone, cabozantinib may fill an unmet need in prostate cancer by synergizing with ICIs.

Cabozantinib (Cabometyx) is approved for treatment of patients with advanced renal cell carcinoma (RCC) and patients with hepatocellular carcinoma (HCC) who have been previously treated with sorafenib¹³. Cabozantinib (Cometriq) is approved for treatment of patients with progressive, metastatic medullary thyroid cancer (MTC)¹⁴. Cabometyx is supplied as a tablet and Cometriq is supplied as a capsule; the two are not equivalent. The most commonly reported ($\geq 25\%$) adverse reactions with cabozantinib (Cabometyx) in RCC studies are: diarrhea, fatigue, nausea, decreased appetite, hypertension, palmar-plantar erythrodysesthesia (PPE), weight decreased, vomiting, dysgeusia, and stomatitis¹⁵. In the COMET-1 study in heavily pre-treated mCRPC patients, the most common ($\geq 25\%$) adverse events with cabozantinib were decreased appetite, nausea, diarrhea, fatigue, vomiting, asthenia, decreased weight, constipation, anemia, PPE syndrome, hypertension, dysphonia, and

dysgeusia¹². SAEs were reported by 62% of patients in the cabozantinib arm. The following SAEs occurred at an incidence of at least 2% higher with cabozantinib compared with prednisone (comparator): pulmonary embolism (6.2% v 0.9%), vomiting (4.1% v 1.8%), fatigue (2.9% v 0.9%), and dehydration (2.9% v 0.3%). Study drug discontinuations because of AEs were reported for 33% of patients in the cabozantinib group. AEs leading to dose reductions or interruptions were reported for 88% of patients in the cabozantinib group, and AEs that led to dose reductions were reported for 67% of patients. Grade 5 AEs occurring within 30 days of the last study drug dose were reported in 15% of patients in the cabozantinib group and were most commonly considered disease related. The authors concluded that the safety data from the COMET-1 trial were consistent with those observed in earlier trials of cabozantinib in mCRPC, with no new or unexpected AEs observed.

2.2 STUDY RATIONALE

The COMET-1 study of cabozantinib in heavily pre-treated metastatic castration-resistant prostate cancer (mCRPC) patients did not meet its primary endpoint of improved overall survival compared with prednisone; however, cabozantinib did demonstrate activity in improving bone scan response, radiographic progression-free survival, symptomatic skeletal events, circulating tumor cell conversions, and bone biomarkers.¹² Furthermore, in subgroup analysis the point estimate of the unstratified hazard ratio for death for those with *visceral* metastases favored cabozantinib (HR=0.77; 95% CI: 0.54 to 1.09). Improved benefit of cabozantinib in visceral disease subgroups has also been demonstrated in two randomized trials in metastatic renal cell carcinoma.^{16,17} While much of the development of cabozantinib in prostate cancer focused on its effects in bone,¹⁸⁻²⁰ we hypothesize that understanding its effects in soft tissue may contribute novel insights and shed light on a possible path forward for further development of cabozantinib in prostate cancer.

Neoadjuvant or pre-surgical studies permit *in vivo* assessment of response and mechanism of action after a short window of treatment.²¹ We have demonstrated the safety and feasibility of using the VEGFR TKI sunitinib in the neoadjuvant or pre-prostatectomy setting.²² Compared with soft tissue and bone biopsies, such an approach has the advantage of providing more plentiful amounts of whole-tumor and stromal tissue for analysis. Cabozantinib may function in prostate cancer partly through modulation of critical stromal interactions within the tumor microenvironment.

Study of the effects of cabozantinib in early stage prostate cancer, specifically in soft tissue prostatectomy specimens, may complement the knowledge gained from ongoing and completed studies in advanced disease. Other groups are currently studying cabozantinib in advanced prostate cancer (mCRPC), with the goals of: (1) determining the lowest effective dose of cabozantinib and correlating bone scan changes with MR imaging ([name], PhD, et al.); (2) developing cabozantinib biomarkers from bone and soft tissue biopsies and comparing 11C-acetate and 18F-fluoride PET/CT to monitor cabozantinib treatment response ([name] and [name], PCF Creativity Award; [name], [name] et al., PCF Challenge award); and (3) investigating bone – tumor interactions and the development of resistance ([name] et al., PCF Challenge award).

Understanding the effects of cabozantinib in soft tissue prostatectomy specimens may also confirm important *in vitro* and *in vivo* observations in prostate cancer models, providing rationale for novel combinations with cabozantinib. For example, emerging data in a chimeric mouse model of mCRPC suggest that cabozantinib may inactivate myeloid derived suppressor cells (MDSCs) and synergize with immune checkpoint blockade (specifically, anti-CTLA4 + anti-PD-1) to overcome *de novo* resistance.⁹ Mechanistically, this stemmed from upregulation of interleukin-1 receptor antagonist and suppression of MDSC-promoting cytokines secreted by prostate cancer cells. A separate study in a pTEN/p53-deficient murine model of advanced prostate cancer has demonstrated that cabozantinib induces tumor clearance by triggering a neutrophil-mediated anti-cancer innate immune response.¹⁰ Cabozantinib also affects M1 macrophage polarization mouse models of prostate cancer.²³ Finally, an *in vivo* and *in vitro* study suggested synergy between cabozantinib and the androgen receptor (AR) signaling inhibitor enzalutamide in CRPC.²⁴ Data like these must be confirmed in prospective clinical trials in humans with prostate cancer.

The HGF/cMET pathway appears to be generally immunosuppressive. MET is expressed by immature CD14+ monocytes which can acquire an immunosuppressive phenotype when exposed to HGF secreted by tumor stromal and/or mesenchymal stem cells. Neutralization of HGF secretion by mesenchymal stem cells reverses this suppression of effector T-cell proliferation and triggers a shift to a TH1-activated T-cell phenotype.^{25,26} Also, HGF secreted by tumor cells and by mesenchymal stem cells can result in the expansion of MDSCs (harboring cMET). This effect is likely mediated, at least in part, by phosphorylation of STAT3 (part of the HGF/cMET signal transduction pathway).²⁵ APC, such as dendritic cells, also express cMET which can be activated by HGF subsequently suppressing APC function, including both antigen presenting capacity and antigen-dependent T-cell responses both *in vitro* and *in vivo*.^{27,28} cMET on tumor cells is associated with VEGF-A production which also has immunosuppressive properties.

In order to provide rationale for combination of cabozantinib with novel immunotherapies and AR-targeted therapies, a hypothesis-generating study of the effects of cabozantinib in soft tissue is clearly warranted. Therefore, with the goal of determining the soft tissue, stromal, cellular, immunologic, molecular and genetic effects of cabozantinib in patients with clinically localized prostate cancer, we propose the following prospective, randomized, open-label, phase II trial of cabozantinib in subjects with untreated, high risk prostate cancer prior to undergoing radical prostatectomy.

2.3 HYPOTHESES

We hypothesize that in those treated with cabozantinib followed by prostatectomy compared with immediate prostatectomy:

1. Apoptotic index (cleaved caspase-3) will be 2-fold higher in prostate cancer tissues following cabozantinib as compared with men proceeding to immediate radical prostatectomy.
2. Infiltration of neutrophils and release of neutrophil chemotactic factors (CXCL12 and HMGB1) will be 2-fold higher in prostate cancer tissues following cabozantinib as compared with men proceeding to immediate radical prostatectomy.

3. Interleukin-1 receptor antagonist will be upregulated and MDSC-promoting cytokines will be suppressed in prostate cancer tissues following cabozantinib as compared with men proceeding to immediate radical prostatectomy.
4. The M1 macrophage population will be decreased without affecting the M2 macrophage population in prostate cancer tissues following cabozantinib as compared with men proceeding to immediate radical prostatectomy.
5. Pathologic complete responses (pCRs) will be observed in the minority population of men harboring the TP53 mutant / PTEN null localized prostate cancer and will be associated with myeloid immune cell activation in the prostate and peripheral blood.

3 OBJECTIVES AND ENDPOINTS

OBJECTIVES	ENDPOINTS	JUSTIFICATION FOR ENDPOINTS
Primary		
To compare pathologic apoptotic indices in prostatectomy specimens from patients who undergo immediate prostatectomy versus those treated with cabozantinib followed by prostatectomy.	Apoptotic index by cleaved caspase-3	To evaluate the activity of cabozantinib in prostate tumors by understanding its ability to cause cell death.
Secondary		
To conduct immune phenotypic profiling on the peripheral blood and tumor microenvironment in prostatectomy specimens from patients who undergo immediate prostatectomy versus those treated with cabozantinib prior to prostatectomy.	
Description of immune biomarkers, including:
 
 • Immune phenotyping of paired peripheral blood and tumor tissue: Myeloid-derived suppressor cells (MDSCs), neutrophils, M1 macrophages, and M2 macrophages in tumor tissue • Immunohistochemical (IHC) analysis of CD8+, programmed death ligand-1 (PD-L1), cytotoxic T-lymphocyte-associated protein 4 (CTLA-4), interleukin-1 receptor antagonist (IL-1RA) and B7H3 in tumor tissue • Neutrophil chemotactic factors (CXCL12 and HMGB1) and MDSC-promoting 	To confirm pre-clinical observations, ^{9,10,23} understand the effects of cabozantinib on the immune microenvironment, and evaluate the rationale for combination of cabozantinib with immune checkpoint inhibitor (ICI) therapy.

OBJECTIVES	ENDPOINTS	JUSTIFICATION FOR ENDPOINTS
	cytokines (CCL5, CCL12, CD40) in tumor tissue	
Exploratory		
1. To estimate the pathologic complete response rate (pCR) and \leq pathologic T2 (\leq pT2) rate in each arm.	1. Rates of pCR and \leq pT2	1. To understand the efficacy of cabozantinib as measured by key clinical pathologic endpoints.
2. To evaluate relapse-free survival in each arm.	2. Relapse-free survival rate at 3 years	2. To understand the efficacy of cabozantinib as measured by a key clinical endpoint.
3. To compare apoptosis (TUNEL), proliferation (Ki-67), and microvessel density (CD31) indices in prostatectomy specimens from patients who undergo immediate prostatectomy versus those treated with cabozantinib prior to prostatectomy.	3. Quantification of TUNEL, Ki-67, and CD31 staining	3. To describe the effects of cabozantinib on tumor tissue as measured by other standard pathologic parameters.
4. To measure expression levels of c-MET, VEGF, and HGF, as well as activation status of c-MET in prostate tissue.	4. Quantification of c-MET, VEGF, HGF, and activated c-MET in prostatectomy tissue	4. To evaluate effects on the c-MET/HGF axis.
5. To describe changes in plasticity signaling markers associated with prostate tumors, including vimentin, AR, SNAIL, AXL, and N-cadherin, with cabozantinib exposure	5. Correlation of changes in vimentin, AR, SNAIL, AXL, and N-cadherin with cabozantinib exposure	5. To describe effects on markers of epithelial-mesenchymal transitions (EMT).
6. To evaluate PTEN and p53 genomic and protein expression status in tumor tissue	6. Measurement of PTEN and p53 genomic and protein expression status in tumor tissue	6. To evaluate whether cabozantinib may be more active in a subset of pTEN/p53-deficient tumors. ¹⁰
7. To demonstrate that cabozantinib is safe and tolerable in patients	7. Adverse events by CTCAE v5.0, dose intensity of cabozantinib.	7. To demonstrate that cabozantinib is safe and tolerable in patients

OBJECTIVES	ENDPOINTS	JUSTIFICATION FOR ENDPOINTS
undergoing radical prostatectomy.		undergoing radical prostatectomy.
8. To demonstrate that surgery is safe and feasible in patients undergoing treatment with cabozantinib.	8. Blood loss at prostatectomy and duration of hospital stay.	8. To demonstrate that surgery is safe and feasible in patients undergoing treatment with cabozantinib.
9. To collect plasma angiome samples (multiplex ELISA) for analysis and correlation with primary and key secondary endpoints.	9. Angiome biomarkers.	9. To collect samples for possible later analysis and correlation with key endpoints
10. To describe gene expression patterns (in particular those associated with apoptosis, androgen receptor signaling, c-MET activation, and a c-MET-specific endocytosis panel) correlated with cabozantinib administration using RNA sequencing analysis.	10. Gene expression patterns.	10. To collect samples for possible later analysis and correlation with key endpoints.
11. To explore changes in serum and intratumoral androgen concentrations related to cabozantinib treatment.	11. Serum and intratumoral androgen concentrations.	11. To collect samples for possible later analysis and correlation with key endpoints.12
12. To collect cell-free DNA (cfDNA) for analysis and correlation with primary and key secondary endpoints.	12. Alterations in cfDNA	12. To collect samples for possible later analysis and correlation with key endpoints.

4 STUDY DESIGN

4.1 OVERALL DESIGN

This is a prospective, randomized, open-label, phase II trial of cabozantinib in subjects with untreated, high risk prostate cancer undergoing radical prostatectomy. This multicenter study will enroll 30 subjects. Duke is the lead site for this trial. There will be a second site selected TBD. Patients will be

assigned or randomized to either: (A) cabozantinib 40 mg PO daily for 4 weeks, followed by a 2 week drug washout period before prostatectomy (n = 20), or (B) immediate prostatectomy (n = 10). The Safety Lead-In Cohort will consist of 6 subjects receiving cabozantinib prior to prostatectomy. The randomized portion will consist of the remaining cabozantinib prior to prostatectomy subjects (n=14) and immediate prostatectomy subjects (n=10).

The first 6 subjects assigned to cabozantinib treatment will constitute the *Safety Lead-In Cohort*, which will be only accrued at Duke. Of these subjects, the first 3 subjects will be enrolled sequentially (that is, after each prior subject completes the day 57-85 safety visit). This will constitute the *Safety Lead-In Cohort Part A*. After 3 cabozantinib treatment patients are accrued sequentially (Part A), the remaining 3 cabozantinib treatment subjects will be accrued non-sequentially, constituting the *Safety Lead-In Cohort Part B*.

If there are ≥ 2 dose-limiting toxicities (DLTs) in the first 6 subjects receiving cabozantinib, the trial will be stopped for safety purposes (*first stopping rule*). DLTs are defined as CTCAE v5 grade ≥ 2 wound dehiscence or wound complication, any grade fistula, grade ≥ 2 hemorrhage of any type, grade ≥ 3 infections [except urinary tract infections (UTIs) which are expected in this population], any AE that leads to permanent discontinuation of cabozantinib, or other grade ≥ 3 cabozantinib-related perioperative complications. The DLT period is defined as day 1 of drug through day 57 of the protocol (inclusive). The seventh subject randomized to cabozantinib may not be enrolled until the sixth subject completes the day 57-85 safety visit and the Duke principal investigator agrees that the stopping rule should not be put into effect.

After six subjects have received cabozantinib and completed the 57-85 day safety visit without triggering a stopping rule, subjects may be accrued at ex-Duke site(s). A *second stopping rule* will be triggered if there are ≥ 3 DLTs in the first 12 subjects treated with cabozantinib. In the event that a stopping rule is triggered, thorough review of the cabozantinib-treated patients' files will be performed and the Duke principal investigator will consider whether the trial can be redesigned or should be permanently discontinued.

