4.5 DEFINITION OF EVALUABLE SUBJECTS

Arm A subjects must complete 21 out of 28 days of planned cabozantinib dosing and proceed to prostatectomy within 14 (+3) days of their last dose of cabozantinib in order to be evaluable for this study's endpoints. Arm B subjects must receive a prostatectomy in order to be evaluable. Subjects who are not evaluable will be replaced.

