6 STUDY ASSESSMENTS

The first 6 subjects assigned to cabozantinib treatment will constitute the *Safety Lead-In cohort*, which will be only accrued at Duke. Of these subjects, the first 3 subjects will be enrolled sequentially (after each prior subject completes the day 57-85 safety visit). This will constitute the *Safety Lead-In Cohort Part A*. After 3 cabozantinib treatment patients are accrued sequentially, the remaining 3 cabozantinib treatment subjects will be accrued non-sequentially, constituting the *Safety Lead-In Cohort Part B*.

If there are ≥ 2 dose-limiting toxicities (DLTs) in the first 6 subjects receiving cabozantinib, the trial will be stopped for safety purposes (*first stopping rule*). DLTs are defined as CTCAE v5 grade ≥ 2 wound dehiscence or wound complication, any grade fistula, grade ≥ 2 hemorrhage of any type, grade ≥ 3 infections [except urinary tract infections (UTIs) which are expected in this population], any AE that leads to permanent discontinuation of cabozantinib, or other grade ≥ 3 cabozantinib-related perioperative complications. The DLT period is defined as day 1 of drug through day 57 of the protocol (inclusive). The seventh subject receiving cabozantinib may not be enrolled until the sixth subject completes the day 57-85 safety visit *and* the Duke principal investigator agrees that the stopping rule should not be put into effect. From the seventh subject on, subjects may be accrued at ex-Duke site(s). A second stopping rule will be triggered if there are ≥ 3 DLTs in the first 12 subjects treated with cabozantinib. In the event that a stopping rule is triggered, thorough review of the cabozantinib-treated patients' files will be performed and the Duke principal investigator will consider whether the trial can be redesigned or should be permanently discontinued.

Subjects assigned or randomized to receive cabozantinib will receive 28 days of study drug. The washout time between the last dose of cabozantinib and surgery will be 14 days (window: +3 days). Reasons for early discontinuation of cabozantinib may include evidence of disease progression, unacceptable toxicity associated with cabozantinib, withdrawal of consent, or other reasons that may impact on the subject's ability to undergo prostatectomy.

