11 STATISTICAL CONSIDERATIONS

11.1 STATISTICAL METHODS

Safety Lead-In and Stopping Rules. The first 6 subjects assigned to cabozantinib treatment will constitute the *Safety Lead-In cohort*, which will be only accrued at Duke. Of these 6 subjects receiving cabozantinib, the first 3 subjects will be enrolled sequentially (after each prior subject completes the day 57-85 safety visit). After this, the remaining 3 subjects receiving cabozantinib may be enrolled non-sequentially in the cohort. If there are ≥ 2 dose-limiting toxicities (DLTs) in the first 6 subjects, the trial will be stopped for safety purposes (*first stopping rule*). DLTs are defined as CTCAE v5 grade ≥ 2 wound dehiscence or wound complication, any grade fistula, grade ≥ 2 hemorrhage of any type, grade ≥ 3 infections [except urinary tract infections (UTIs) which are expected in this population], any AE that leads to permanent discontinuation of cabozantinib, or other grade ≥ 3 cabozantinib-related

perioperative complications. The DLT period is defined as day 1 of drug through day 57 of the protocol (inclusive). The seventh subject randomized to cabozantinib may not be enrolled until the sixth subject completes the day 57-85 safety visit and the Duke principal investigator agrees that the stopping rule should not be put into effect. From the seventh subject on, subjects may be accrued at ex-Duke site(s). A *second stopping rule* will be triggered if there are ≥ 3 DLTs in the first 12 subjects treated with cabozantinib. In the event that a stopping rule is triggered, thorough review of the cabozantinib-treated patients' files will be performed and the Duke principal investigator will consider whether the trial can be redesigned or should be permanently discontinued.

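### A cabozantinib-related event that arises after the last dose and prevents prostatectomy meets no DLT criterion unless it is a wound event, fistula, hemorrhage or infection, so it adds nothing to the 2-of-6 or 3-of-12 stopping count (minor)

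*Combined protocol and SAP*

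**What the plan says.** The DLT definition appears in Sections 4.1, 6 and 11.1 with the same list. Four items are defined by type of event: wound dehiscence or complication at grade 2 or above, fistula of any grade, hemorrhage at grade 2 or above, and infection other than UTI at grade 3 or above. The fifth and sixth items follow in Section 4.1: "any AE that leads to permanent discontinuation of cabozantinib, or other grade" 3 or higher "cabozantinib-related perioperative complications". Section 11.1 repeats the fifth as "any AE that leads to permanent discontinuation of cabozantinib". The sixth is a residual item, and the word *perioperative* is not defined.

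On timing, Section 4.1 states: "The DLT period is defined as day 1 of drug through day 57 of the protocol (inclusive"). Section 6 states: "Subjects assigned or randomized to receive cabozantinib will receive 28 days of study drug", and "The washout time between the last dose of cabozantinib and surgery will be 14 days (window: +3 days").

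Section 6 also lists, among the grounds for stopping the drug early, reasons that may affect the subject's "ability to undergo prostatectomy". Section 4.5 makes surgery a condition of being evaluable in Arm A and adds: "Subjects who are not evaluable will be replaced".

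The first rule triggers at 2 or more DLTs in the first 6 men given cabozantinib, the second at 3 or more in the first 12. After a trigger the lead principal investigator reviews the files and decides between redesign and closure.

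**The concern.** The window deliberately extends past dosing, but one of the two general routes to a DLT closes when dosing ends. Before Day 28, an event serious enough to end treatment counts whatever its type or grade. After Day 28, the same kind of event must qualify as a perioperative complication.

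The difficulty is sharpest when the event means that no operation takes place. Suppose a man has a drug-related myocardial infarction or drug-induced liver injury a week after his last dose and surgery is cancelled. Sections 7.4.2.5 and 7.4.2.12 would have required the drug to be stopped had he still been taking it, and that would have been a DLT. In the washout he meets no listed item on a plain reading. He is replaced, and the count does not change.

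Loss of curative surgery through a drug effect is a central harm in a pre-surgical trial, and exploratory objective 8 is to show that surgery is feasible after cabozantinib. The first rule also controls entry of the seventh cabozantinib subject and the opening of sites other than the lead site. If one DLT has already been counted among the first 6, whether this event counts decides between 1 of 6 and 2 of 6.

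**Working it through.** **Nothing to reproduce for the stopping rules.** The protocol gives no operating characteristics for them. Its only operating figures are the 70% and 96% power of the primary t-test. These reproduce (70.3% and 96.2%) but do not bear on this point.

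**Step 1: which items can still apply after the last dose and before surgery.**

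| DLT item | Can it be met in the washout? |
|---|---|
| Wound event, fistula, hemorrhage, non-UTI infection | Yes, by type and grade |
| AE leading to permanent discontinuation | No, dosing is over |
| Other related grade 3+ perioperative complication, surgery goes ahead | Reasonably yes |
| Same item, event prevents surgery | Does not fit |

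**Step 2: the interval.** With the last dose on Day 28 and surgery on Day 43 (+3), the interval is Days 29 to 42, or up to Day 45. That is 14/57 = 25% to 17/57 = 30% of the DLT window. This is the time over which the question can arise, not coverage lost, because four items apply throughout.

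**Step 3: is a drug-related event plausible then?** Section 4.3 gives a half-life of about 120 hours, or 5 days. The fraction remaining is 0.5^(14/5) = 0.144 at 14 days and 0.5^(17/5) = 0.095 at 17 days. Exposure is falling but not negligible.

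**Step 4: effect on the rules.** Let p be the chance that a man has a DLT that counts now, and q the chance that he has an event that does not count now. The documents give neither, so both are assumptions. With independence and at most one DLT per man, the rate after the change is p' = 1 − (1 − p)(1 − q). With X the number in the first 6 men and Y in the next 6, each Binomial(6, p'):

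P(either rule triggers) = 1 − [P(X=0)·P(Y≤2) + P(X=1)·P(Y≤1)]

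Example, p = 0.10 and q = 0: 1 − [0.5314 × 0.9842 + 0.3543 × 0.8857] = 0.163.

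With q = 0.01, p' = 1 − 0.90 × 0.99 = 0.109: 1 − [0.5003 × 0.9799 + 0.3673 × 0.8676] = 0.191.

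| p | q = 0 | q = 0.5% | q = 1% | q = 2% |
|---|---|---|---|---|
| 5% | 4.2% | 5.1% | 6.0% | 8.0% |
| 10% | 16.3% | 17.7% | 19.1% | 22.0% |
| 20% | 50.6% | 52.0% | 53.3% | 55.9% |

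The increase is about 1 percentage point at q = 0.5%, 2 to 3 at 1%, and 4 to 6 at 2%.

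**Step 5: how often it could decide a rule.** The chance of at least one such event in 12 men is 1 − (1 − q)^12 = 6%, 11% and 22% for the three values of q. If one of the first 6 men already has a DLT, the chance of such an event among the other 5 is 1 − (1 − q)^5 = 2%, 5% and 10%. If 2 of 12 do, it is 1 − (1 − q)^10 = 5%, 10% and 18%. These last two sets are conditional on already being one short of a threshold and are not overall effects.

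**The case against.** The strongest reply is that the gap needs a narrow reading. The window runs to Day 57 by design, the drug is given only as a lead-in to surgery, and the last item is written as a residual clause. A related grade 3 event in a man awaiting surgery in the next two weeks is perioperative in an ordinary sense. This stands for men who go on to surgery. A reader might infer that every serious systemic event in the washout escapes the rules; the documents do not support that. The reply is weakest when there is no operation for the event to surround.

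The second reply is that such an event would not go unnoticed. Section 10.3 provides reviews after 6, 12 and 18 treated men. Section 13.1 has the principal investigator monitoring continuously, with closure possible for an unexpected frequency of grade III or IV events. Related SAEs are reported within one business day (10.1.4), the first 3 men enter one at a time, and the principal investigator must agree before the seventh cabozantinib subject enrolls. A triggered rule leads to review, not automatic closure. All of this stands as protection against missing the event. None of it adds the event to the count: Section 10.3 describes its monitoring as separate from the stopping rules, and neither section sets a number.

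Two other inferences should be resisted. The 25% to 30% of DLT days is not lost coverage, since wound events, fistula, hemorrhage and non-UTI infection count on each of those days. Nor does replacement remove a man from the denominator: the rules refer to the first 6 and first 12 men given cabozantinib, and he remains one of them. What is missing is his event in the numerator.

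**Conclusion.** The point holds for a cabozantinib-related AE that first arises after the last dose, prevents prostatectomy, and is not a wound event, fistula, hemorrhage or infection already listed. It meets no DLT item on a plain reading, and the man is replaced without adding to either count. For washout events followed by surgery, the residual item can reasonably be read to apply, so the issue there is only an undefined word.

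The expected effect is small: about 1 to 6 percentage points on the chance that a rule triggers, for counted DLT rates of 5%, 10% and 20% and uncounted rates of 0.5% to 2%. All these rates are assumptions; a larger uncounted rate would give a larger shift. The case for the change rests on fixing in advance how a rare but serious event is counted, not on the average shift. Priority: minor.

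**What to change.** In Sections 4.1, 6 and 11.1, replace the last DLT item with:

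*any other cabozantinib-related grade ≥3 AE with onset from the last dose of cabozantinib through Day 57, whether or not surgery takes place, or any cabozantinib-related AE that prevents prostatectomy; events attributed solely to the prostatectomy are not counted under this item.*

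This ties counting to grade, timing and attribution. It avoids asking after the event whether the drug would have been stopped had dosing continued. The final clause is consistent with Section 10.1.4, which does not collect SAEs due solely to the operation.

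The cost is one replaced item in three places, with no new visits or tests. The rules become slightly more likely to trigger (2 to 3 percentage points if such events occur in 1% of men), and the investigator must judge attribution to cabozantinib, including for low-grade events that prevent surgery. If the sponsor already reads *perioperative* broadly, the first half only writes that reading down and the real change is the surgery-prevented case.
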